3.2 Study Population

For entry into the study, the following criteria MUST be met.

3.2.1 Inclusion Criteria

1) Signed Written Informed Consent

- Before any study procedures are performed, subjects will have the details of the study described to them, and they will be given a written informed consent document to read. Then, if subjects consent to participate in the study, they will indicate that consent by signing and dating the informed consent document in the presence of study personnel.

2) Target Population

- Subjects with a diagnosis of Type 2 diabetes mellitus within the previous 15 years using criteria of the American Diabetes Association.

- Currently treated with Insulin (long or short acting or combination), Metformin (stable dose of 1-2 grams/day), or a stable dose of both.
- HbA1C between 6.5% and 10% (both inclusive)
- BMI 25-39.9 kg/m² both inclusive.
- History of Stage 1-3 CKD shown by a laboratory test taken within the past 2 years

CKD Staging:

Estimated Glomerular Filtration Rate Serum Cr should be used to estimate glomerular filtration rate (GFR). Estimated GFR (eGFR) is commonly reported by laboratories or can be estimated using formulae such as the Modification of Diet in Renal Disease (MDRD) study equation or the Chronic Kidney Disease Epidemiology Collaboration (CKD-EPI) equation. The latter is the preferred GFR estimating equation. GFR calculators are available at [http:// www.nkdep.nih.gov](http://www.nkdep.nih.gov).

Abnormal urinary albumin excretion and eGFR may be used to stage chronic kidney disease (CKD). The National Kidney Foundation classification (Table below) is based on **both kidney damage (UACR at or above 30 mg/g Cr) and eGFR.**

Normal UACR is defined as less than 30 mg/g Cr, and increased urinary albumin excretion is defined as at or above 30 mg/g Cr. Because of variability in urinary albumin excretion, ideally two (at least one) specimens of UACR should have been collected within a 3- to 6-month period before considering a patient to have albuminuria.

Stage -- Description -- GFR (mL/min/1.73 m²)

Stage 1 Kidney damage* with normal or increased GFR \geq 90

2 Kidney damage* with mildly decreased eGFR 60–89

3 Moderately decreased eGFR 30–59

4 Severely decreased eGFR 15–29

5 Kidney failure ,15 or dialysis

*Kidney damage is defined as abnormalities on pathological, urine, blood, or imaging tests.¹

3) Age and Reproductive Status

Men and women, 40 to 70 years of age.

- Enrolled women must not be pregnant, should not be breast-feeding and should not be taking hormone replacement therapy (HRT) during randomization.

The following women are WOCBP:

- Women using the following methods to prevent pregnancy: Oral contraceptives, other hormonal contraceptives (vaginal products, skin patches, or implanted or injectable products), or mechanical products such as intrauterine devices or barrier methods (diaphragm, condoms, spermicides).
- Women who are practicing abstinence.

- Women who have a partner who is sterile (e.g., due to vasectomy). WOCBP must be using an acceptable method of contraception to avoid pregnancy throughout the study and for up to 4 weeks after the last dose of study drug in such a manner that the risk of pregnancy is minimized.
- WOCBP must have a negative serum or urine pregnancy test result (minimum sensitivity 25 IU/L or equivalent units of HCG) within 0 to 72 hours before the first dose of study drug.
- Women must not be breast-feeding.

Post-menopause is defined as:

- Women who have had amenorrhea for ≥ 12 consecutive months (without another cause) and/or who have a documented serum follicle-stimulating hormone (FSH) level > 35 mIU/mL.
- Women who have irregular menstrual periods and a documented serum FSH level > 35 mIU/mL.
- Women who are taking hormone replacement therapy (HRT).

3.2.2 Exclusion Criteria

- Type 1 diabetes mellitus
- History of diabetic ketoacidosis or hyperosmolar non-ketotic coma
- Low hematocrit (< 28 Units)
- History of pancreatitis, or cancer (except basal cell carcinoma and cancer that is cured or not active or being treated in the past five years)
- Previous coronary event or history of cerebrovascular event within 6 months of screening or active or clinically significant coronary and/or peripheral vascular disease
- CKD Stages 4 and 5 (estimated CrCl < 30 mL/min)
- Beginning Statin medications or of change of Statin dose in the last 3 months,
- Use of oral or injectable anti-diabetic medication other than Insulin and Metformin. We did not want to bring in too many variables in the control arm and wanted to avoid a combination of insulin and other OHAs as the results might be difficult to interpret.
- Patients will be off other OHA (other than Metformin) before randomization and inclusion in the study.
- Use of consistent long-term steroid medication (oral, inhaled, injected) within the last 3 months
- Untreated Systolic BP > 140 mmHg and Diastolic BP > 90 mmHg
- Active wounds or recent surgery within 3 months
- Inflammatory disease, or current chronic use of anti-inflammatory drugs in the last 3 months.

- Untreated hyper/hypothyroidism
- Contraindications for moderate exercise
- Implanted devices (e.g., pacemakers) that may interact with Tanita scale

Physical and Laboratory Test Findings

- Pre-existing liver disease and/or ALT and AST >2.5X's UNL,
- serum creatinine levels ≥ 2.0 with estimated CrCl < 30 mL/min)
- Triglycerides >450 mg/dL

Allergies and Adverse Drug Reactions

- Subjects with a history of any serious hypersensitivity reaction to Linagliptin or another DPP-4 inhibitor.

Sex and Reproductive Status

- Women in reproductive age group will be included in the study but encouraged to use contraceptive method to avoid pregnancy within 16 weeks of study duration.
- Women who are pregnant or breast-feeding will be excluded.

Prohibited Treatments and/or Therapies

Treatment with a strong cytochrome P450 3A4 (CYP3A4) or P-gp inducer (i.e. rifampin)

Other Exclusion Criteria

- Prisoners or subjects who are involuntarily incarcerated.
- Subjects who are compulsorily detained for treatment of either a psychiatric or physical (e.g., infectious disease) illness.

Additionally, patients who are active smokers, patients who are pregnant, nursing women, and women who are on hormone replacement therapy will be excluded. Patients on low dose oral contraceptives will be allowed to participate as these formulations contain very low amounts of estrogens.

Eligibility criteria for this study have been carefully considered to ensure the safety of the study subjects and to ensure that the results of the study can be used. It is imperative that subjects fully meet all eligibility criteria.

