Study Design:	Prospective, double-masked, randomized placebo-controlled trial
Accrual Goal: (Total number of subjects)	N=40
Accrual Rate: (Number of subjects expected per month)	Recruit 40 patients in approximately 36 months.
Estimated: FPFV: LPFV: Follow Up: (dd-mm-yy)	FPFV: 09-15-2015. LPFV: 09-15-2018
Co-relative Studies: (PK/PD, etc.)	N/A
Inclusion Criteria:	
 1. Adults aged 40-70 years. 2. Diagnosis of type 2 diabetes within the previous 15 years using criteria of the American Diabetes Association 3. Currently treated with a stable dose of Insulin, Metformin (1-2 grams/day), or a stable combination of the two as therapy. 4. HbA1C between 6.5 to 10% (both inclusive) 5. BMI 25 to 39.9 kg/m² (both inclusive) 6. CKD stages 1-3

Exclusion Criteria:
	
Patients with:
 
 1. Implanted devices (e.g., pacemakers) that may interact with Tanita scale 2. Previous coronary or cerebrovascular event within 6 months of screening or active or clinically significant coronary and/or peripheral vascular disease 3. Low hematocrit (<28 UNITS). 4. Pre-existing liver disease and/or ALT and AST >2.5X's UNL 5. CKD stage 4 and 6. History of pancreatitis, or cancer (except basal cell carcinoma and cancer that is cured or not active or being treated in the past five years) 7. Statin use started or dose change in the last 3 months 8. Use of oral anti-diabetic medication other than Metformin, or Insulin. 9. Use of consistent long-term steroid medication in the last 3 months (oral, inhaled, injected). 10. Systolic BP> 140 mmHg and Diastolic BP> 90 mmHg 11. Active wounds or recent surgery within 3 months. 12. Inflammatory disease, or chronic current use of anti-inflammatory drugs within the last 3 months 13. triglycerides >450 mg/dL 14. untreated hyper/hypothyroidism 15. Auto antibody confirmed type 1 diabetes 
Additionally, patients who are active smokers, patients who are pregnant, nursing women, and post-menopausal women who are on hormone replacement therapy will be excluded.
 
Patients on low dose oral contraceptives will be allowed to participate as these formulations contain lesser amount of estrogens.

-----------------------------------	---

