3.2.3 Discontinuation of Subjects from Treatment

Subjects MUST discontinue investigational product (and non-investigational product at the discretion of the investigator) for any of the following reasons:

- Withdrawal of informed consent (subject's decision to withdraw for any reason).
- Any clinical adverse event, laboratory abnormality, or inter-current illness which, in the opinion of the investigator, indicates that continued participation in the study is not in the best interest of the subject.

- Patients in CKD stages 1-3 who progress to stages 4 and beyond, post screening, will be excluded also.
- Concomitant treatment with a strong systemic cytochrome P450 3A4 (CYP 3A4) or P-gp inducer such as rifampicin. Use of alternative treatments to Linagliptin is recommended.
- Pregnancy
 - Pregnant patients will be advised to contact the investigator or study staff immediately if they suspect they might be pregnant (e.g., missed or late menstrual period) at any time during study participation.
- Loss of ability to freely provide consent through imprisonment or involuntary incarceration for treatment of either a psychiatric or physical (e.g., infectious disease) illness.
- If pancreatitis is suspected, promptly discontinue treatment with Linagliptin

All subjects who discontinue should comply with protocol-specified follow-up procedures outlined before. The only exception to this requirement is when a subject withdraws consent for all study procedures or loses the ability to consent freely (i.e., is imprisoned or involuntarily incarcerated for the treatment of either a psychiatric or physical illness). If a subject withdraws before completing the study, the reason for withdrawal must be documented appropriately.

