4.4 Blinding/ Unblinding

Blinding is critical to the integrity of this clinical study. However, in the event of a medical emergency or pregnancy in a subject, **in which knowledge of the investigational product is critical to the subject's management**, the blind **for that subject** may be broken.

Before breaking the blind of an individual subject's treatment, the investigator should have determined that the information is necessary, i.e., that it will alter the subject's immediate management. In many cases, particularly when the emergency is not investigational product-related, the problem may be properly managed by assuming that the subject is receiving active product without the need for un-blinding.

End of Study Unblinding Protocol

Upon completion of the research study, we will undergo the following protocol in order to unblind the research data.

Unblinding is the process by which the allocation code is broken so that the investigator, clinical staff and the trial statistician becomes aware of which intervention each subject enrolled in the research study was taking.

Unblinding at the end of the study is required in order to make unmasked analysis in accordance with the study analysis plan. It is also conducted in order to inform the participants of which investigational product they were assigned to.

Time to unblind:

Unblinding shall be conducted when all subjects enrolled in the research study have finished treatment, and all follow up visits. There must be no plan to recruit any more subjects in the research study. Additionally, all data points and outcome measures for each research subject must have been collected, and ideally compiled. Prior to unblinding there will be a data lock on clinical outcome measures and basic side outcome measures and associated research data collected for the study.

Procedure to unblind

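### Contraception is a condition of entry in Section 3.2.1 but only encouraged in Section 3.2.2, and the protocol does not say which rule governs

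*Combined protocol and SAP*

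**What the plan says.** Section 3.2.1 (Inclusion Criteria, Age and Reproductive Status) states: "WOCBP must be using an acceptable method of contraception to avoid pregnancy throughout the study and for up to 4 weeks", the 4 weeks being counted from the last dose of study drug. The term is introduced by "The following women are WOCBP", followed by three groups: women using hormonal, mechanical or barrier methods; women who are abstinent; and women whose partner is sterile. The same section requires WOCBP to have a negative pregnancy test in the 72 hours before the first dose.

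Section 3.2.2 (Exclusion Criteria, Sex and Reproductive Status) states: "Women in reproductive age group will be included in the study but encouraged to use contraceptive method to avoid pregnancy within 16 weeks", the 16 weeks being described as the study's duration.

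Both sections are presented as binding. Section 3.2 opens with "For entry into the study, the following criteria MUST be met", and Section 3.2.2 closes with "It is imperative that subjects fully meet all eligibility criteria". The only other eligibility text on contraceptives concerns low-dose oral products. The Protocol Synopsis has "Patients on low dose oral contraceptives will be allowed to participate as these formulations contain lesser amount of estrogens", and Section 3.2.2 has a near-identical sentence. That permits one method; it does not say whether a method is required.

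**The concern.** Two adjacent eligibility sections give different answers for the same woman. One bars a fertile woman who will not use contraception. The other says she is included and advises her to use it. No text reconciles them.

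The stake is patient safety. The protocol takes pregnancy on study drug seriously. Section 3.2.3 lists it under "Subjects MUST discontinue investigational product (and non-investigational product at the discretion of the investigator) for any of the following reasons", and Section 4.4 allows one subject's blind to be broken "in the event of a medical emergency or pregnancy in a subject" where knowing the treatment is critical to her care. Those provisions act once a pregnancy is known or suspected. The contraception rule is the only one meant to prevent it, so it should not read as compulsory in one section and optional in the next.

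**Working it through.** No statistical figure is involved, so the check is a comparison of texts plus one count of weeks.

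**Step 1: apply each rule to the same woman.**

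| Woman screened | Section 3.2.1 | Section 3.2.2 |
|---|---|---|
| Fertile, uses contraception | May enter | May enter |
| Fertile, uses none; WOCBP taken in its ordinary sense | May not enter | Included, with advice |
| Same woman; the WOCBP list taken as closed | Not addressed | Included, with advice |

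The rules agree on the first row and part on the second. The third row arises because the three listed groups are all women who already have some protection against pregnancy. The list is not worded as exclusive, and the usual meaning of the term covers the woman in question, so the second row is the better reading. Still, read literally, Section 3.2.2 is the only rule that reaches her, and it lets her in.

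**Step 2: compare the time windows.** Dosing lasts 12 weeks (Section 3.1).
- Section 3.2.1, counted from the first dose: 12 + 4 = up to 16 weeks.
- Section 3.2.2, if its 16 weeks run from the first dose: the same 16 weeks.
- Section 3.2.2, if its 16 weeks run from screening at week -4: 4 + 12 = 16, ending at the last dose and covering none of the 4 weeks after it. Section 3.1 appears to count this way when it gives 16 weeks of lifestyle modification against 12 of treatment.

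The windows may or may not agree. The difference in obligation remains either way.

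**Step 3: see what the other safeguards cover.**
- A negative test is mandatory for WOCBP before the first dose (Section 3.2.1), and pregnant women are excluded outright (Section 3.2.2).
- The Section 4.5 schedule lists a urine test at screening and at weeks 0, 6 and 12, marked as needed. The list of measures that follows directs urine pregnancy testing to women of childbearing potential.
- Subjects are told to contact staff at once if they suspect pregnancy, and study drug is then stopped (Section 3.2.3).

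These measures detect pregnancy and shorten exposure. On-treatment tests are 6 weeks apart, so a conception between visits could be exposed to study drug for some weeks before a scheduled test finds it.

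**The case against.** The strongest reply is that the protocol already resolves the conflict. Eligibility criteria are cumulative: every one has to be met. A woman who satisfies Section 3.2.1 also satisfies Section 3.2.2, but not the reverse, so the stricter rule governs. The methods text in Section 4.5 also has staff confirm at week 0 that the inclusion criteria still hold, and the contraception requirement sits among them. On this view, the Section 3.2.2 sentence excludes nobody and means only that reproductive age is not itself a bar.

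Most of this stands. It is the better reading, and enrolling a woman on Section 3.2.2 alone would breach Section 3.2.1. Two things remain. The protocol leaves the reader to infer this result, against a sentence that positively says these women are included. And the inference depends on the woman being a WOCBP, a term whose list does not name her. Staff should not have to infer a safety criterion.

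A second reply is that few women are at issue and that they are well monitored. That is fair: eligible ages are 40 to 70, and the testing is real. It limits how serious the point is, but it does not reconcile the wording.

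**Conclusion.** The inconsistency is real and narrow. Section 3.2.1 requires contraception and Section 3.2.2 only encourages it. The protocol favours the stricter rule without saying so, and a fertile woman using no contraception could be enrolled and dosed on the wording of Section 3.2.2. The number affected cannot be estimated from the documents and could be zero. It should be corrected because it concerns subject safety and costs almost nothing.

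Four stronger inferences are not supported:
- *That the protocol permits unprotected dosing outright.* The requirement that all criteria be met points the other way.
- *That pregnancy testing is also missing.* The pre-dose test is mandatory for WOCBP, and later tests are scheduled and directed at women of childbearing potential.
- *That different sites would apply different rules.* The Protocol Synopsis names one site, and the Veterans Affairs clinics only refer patients. The risk is one team misreading its own protocol.
- *That a pregnancy would threaten the trial's power.* Subjects who stop drug are still asked to complete follow-up (Section 3.2.3), and the mixed models of Section 5 can use incomplete records. There is no effect on sample size, power or analysis.

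The conclusion assumes that a fertile woman not using contraception could present for screening, which the age range and the plan to include women of reproductive age both allow.

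**What to change.** Make two wording changes.

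1. In Section 3.2.2, replace the sentence that encourages contraception with the Section 3.2.1 requirement: WOCBP must use an acceptable method for the whole study and up to 4 weeks past their last dose. This also removes the doubt about where the 16 weeks begin.
2. In Section 3.2.1, introduce the list with a general definition: WOCBP are all women who are not post-menopausal or otherwise unable to conceive, including the three groups named. The section already defines post-menopause.

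The testing schedule can stay as it is.

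The cost is a protocol amendment to two sentences, with no added visits or procedures. The one practical downside is that fertile women who decline contraception cannot enter. Their number is unknown, and Section 3.2.1 already intends to keep them out.

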3.2.3 Discontinuation of Subjects from Treatment

Subjects MUST discontinue investigational product (and non-investigational product at the discretion of the investigator) for any of the following reasons:

- Withdrawal of informed consent (subject's decision to withdraw for any reason).
- Any clinical adverse event, laboratory abnormality, or inter-current illness which, in the opinion of the investigator, indicates that continued participation in the study is not in the best interest of the subject.

- Patients in CKD stages 1-3 who progress to stages 4 and beyond, post screening, will be excluded also.
- Concomitant treatment with a strong systemic cytochrome P450 3A4 (CYP 3A4) or P-gp inducer such as rifampicin. Use of alternative treatments to Linagliptin is recommended.
- Pregnancy
 - Pregnant patients will be advised to contact the investigator or study staff immediately if they suspect they might be pregnant (e.g., missed or late menstrual period) at any time during study participation.
- Loss of ability to freely provide consent through imprisonment or involuntary incarceration for treatment of either a psychiatric or physical (e.g., infectious disease) illness.
- If pancreatitis is suspected, promptly discontinue treatment with Linagliptin

All subjects who discontinue should comply with protocol-specified follow-up procedures outlined before. The only exception to this requirement is when a subject withdraws consent for all study procedures or loses the ability to consent freely (i.e., is imprisoned or involuntarily incarcerated for the treatment of either a psychiatric or physical illness). If a subject withdraws before completing the study, the reason for withdrawal must be documented appropriately.

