
Criteria for Evaluation: (Efficacy, safety, stopping rules, etc.)
	
Subjects will be screened at week -4, then evaluated for end points at weeks 0, 6 and 12. Follow up phone call will be done 30 days after last dose of study drug to assess for adverse effects.
 
Study participation will be stopped for adverse effects at the discretion of the study investigator. Subjects may stop study participation at any time and for any reason.

Statistics:
	
The total sample size is requested, after accounting for attrition over the 12-week period, is 20 subjects per group or 40 subjects total. Sample size estimates were based on the effects of exercise on CD34+/KDR+ cells as described in the literature. The effect of a single session, as well as extended training, on healthy subjects or those with existing cardiovascular conditions appears to increase the CD34+/KDR+ cells.
 
This is a pilot study as a result appropriate power calculation is not feasible. We however did conduct power analysis, which provided us with 73% power (see statistics section). A p-value of less than 0.05 will be considered statistically significant.

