In this proposed study we plan to recruit patients with type 2 diabetes of ≤ 15 years duration (in early phase of diagnosis), who are on a stable dose of insulin, Metformin, or both for at least 3 months either short or long acting but still remain inadequately controlled with HbA1C between 6.5% and 10% (both values inclusive), but not overtly out of control ($> 10\%$ of HbA1C).

The patient will adjust insulin levels so as to keep their HbA1C levels under 10.0%, for health measures. If the HbA1c rises above 10.0% then the PI will speak with the patient and provide a documented form indicating the insulin dose adjustment that should be

made. Initially life-style intervention with diet and regular aerobic activity (as per Standards of Diabetes Care: Diabetes Care Supplement: Jan 2014) along with insulin titration will be undertaken for initial 4 weeks (time between screening visit and 1st visit). Subjects will begin taking 5.0 mg of Linagliptin or placebo after initial 4 weeks. Subjects will be withdrawn from the study if the medication or placebo is not tolerated.

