2 STUDY OBJECTIVES

2.1 Primary Objective

To investigate the effect of Linagliptin on Endothelial progenitor cells (CD34 positive cells) in patients whose HbA1C is between 6.5 to 10% (both inclusive) while being on treatment with a stable dose of insulin, Metformin, or both for the preceding 3 months before enrollment.

Cellular markers: We will use patient's peripheral blood derived CD34+ cells looking at number, function and gene expression changes pre and post Linagliptin over 12 weeks of therapy.

Urinary Function Marker in CKD: We will estimate 24hr urinary protein estimation and creatinine clearance (This is measured via the micro-albumin/Creatinine ratio provided from a random spot urine sample).

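### Section 1 and the synopsis take patients with intolerance or adverse effects out of the study, Section 3.2.3 keeps them in follow-up, and the CKD-progression rule is ambiguous between the two

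*Combined protocol and SAP*

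**What the plan says.** Three places deal with patients who cannot or should not continue.

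- Section 1 (Research Hypothesis), on intolerance: "Subjects will be withdrawn from the study if the medication or placebo is not tolerated".
- Protocol synopsis, Criteria for Evaluation: "Study participation will be stopped for adverse effects at the discretion of the study investigator".
- Section 3.2.3, whose list opens with "Subjects MUST discontinue investigational product (and non-investigational product at the discretion of the investigator) for any of the following reasons". One item in that list reads "Patients in CKD stages 1-3 who progress to stages 4 and beyond, post screening, will be excluded also". After the list comes the follow-up rule: "All subjects who discontinue should comply with protocol-specified follow-up procedures outlined before". Its scope is then fixed: "The only exception to this requirement is when a subject withdraws consent for all study procedures or loses the ability to consent freely".

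Two other places bear on the CKD item. Section 3.2.2 defines the threshold as "CKD Stages 4 and 5 (estimated CrCl < 30 mL/min", and Section 2.1 lists a renal measure under the primary objective: "We will estimate 24hr urinary protein estimation and creatinine clearance". Section 2.2 names creatinine clearance again as a secondary measure.

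Section 5 plans a linear mixed model and notes its advantage over ANOVA when data are missing. It defines no analysis set and gives no rule for patients who leave early.

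**The concern.** Stopping study drug and leaving the study are different events. In a randomised comparison only the second has to cost outcome data. Here the documents use both for similar situations, so site staff cannot tell whether a patient who stops the drug in week 3 for intolerance should return at weeks 6 and 12.

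If Section 1 and the synopsis are followed as written, later outcomes are lost for reasons that may be linked to the treatment. If the CKD item is read as leaving the study, the reason may also be linked to an outcome. Such losses can disturb the comparison that randomisation set up, and with 20 patients per arm a missed week-12 value cannot be recovered later.

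**Working it through.** The point rests on the wording, so the check sets the rules side by side.

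**Step 1. What each rule ends, and whether the follow-up rule exempts it.**

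| Trigger | Place | What ends | Exempt from follow-up under 3.2.3? |
|---|---|---|---|
| Intolerance | Section 1 | The study | No |
| Adverse effects, at investigator discretion | Synopsis | Study participation | No |
| Progression to CKD stage 4 or beyond | 3.2.3 list | Unclear | No |
| Consent withdrawn for all procedures | 3.2.3 | All procedures | Yes |
| Ability to consent freely lost | 3.2.3 | All procedures | Yes |

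The first two rows contradict the follow-up rule. Intolerance against Section 3.2.3 is the plainest case.

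**Step 2. What follow-up means.** Section 3.2.3 points back to procedures already described. The only contact described for the period after treatment is a safety telephone call about a month after dosing ends. The week-6 and week-12 assessments are also described earlier, so the rule could include them. The Section 4.5 schedule has no early-termination visit and does not say whether those two visits apply to a patient off drug.

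**Step 3. The CKD item.** Three readings fit the text.

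- Stop study drug: the item sits in a list of reasons for doing exactly that.
- Fail eligibility before randomisation: the item speaks of the time after screening, four weeks separate screening from week 0, and Section 4.5 re-checks the inclusion criteria at week 0.
- Leave the study: the ordinary sense of the word used.

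The trigger is tied to a named outcome through creatinine clearance. The tie is loose: Section 3.2.1 stages CKD by eGFR, while Section 2.1 says its renal measure comes from a spot-urine albumin/creatinine ratio. It does not apply to intolerance.

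**Step 4. What a literal reading loses.** Outcomes are measured at weeks 0, 6 and 12.

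- Withdrawn before week 6: both post-baseline visits are lost, and the patient contributes nothing to the estimated change.
- Withdrawn between weeks 6 and 12: one visit is lost.
- Trigger found on the week-12 sample: no scheduled efficacy visit is lost.

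**Step 5. Size.** The documents give no rate of intolerance, withdrawal for adverse effects or CKD progression. For the CKD item only, a simulation shows what could happen. All of its inputs are assumptions, not figures from the documents: eGFR uniform on 30–100 or 30–60; within-patient SD 4 or 8; control change of −2 mL/min by week 12, half of it by week 6; true effect 0 or +5 mL/min; baseline value at least 30.

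- Control patients with a value below 30 at week 6 or 12: 4% to 18%. Treated patients, if the effect is +5: 1% to 10%.
- Those patients removed from the analysis altogether: a true +5 is estimated as about 4.3 to 4.9.
- Only week 12 lost after a week-6 value below 30: about 4.9 to 5.0.
- No true effect: bias about 0 in every setting.

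So under these assumptions, deleting patients matters more than missing a later visit.

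**The case against.** The strongest reply is that Section 3.2.3, read in context, already keeps patients who progress to stage 4: the item concerns investigational product, the follow-up rule covers everyone in the list, and CKD progression is not an exception. That is a fair reading. It means the CKD item cannot be presented as a clear instruction to remove randomised patients. It does not settle the matter, because the item uses a word that elsewhere in the protocol concerns entry to the study.

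A reader might infer that every patient reaching stage 4 is lost and that the renal outcome is cut off at its worst values. The documents do not support this. Scheduled laboratory tests after randomisation fall at weeks 0, 6 and 12, so the triggering value would usually be in hand already. Nothing says that collected data are deleted, and the mixed model can use incomplete records. If the triggering value is kept, later loss can be accommodated under missing at random.

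A reader might also size the problem as lost power, taking the 25% attrition in Section 5 to leave 20 × 0.75 = 15 per arm. That does not follow. Section 5 attaches the 25% to screening 55 patients (55 × 0.75 = 41.25, close to the 40 planned) and separately plans for 18 completers out of 20, a loss of 2/20 = 10%. No part of either figure is attributed to these rules.

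Finally, the investigator may properly judge that further participation is not in a patient's interest, and the visits include a substantial blood draw. That stands, and the fix must respect it.

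None of this removes the conflict between Section 1, the synopsis and the follow-up rule.

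**Conclusion.** The conflict is real. Section 1 and the synopsis end study participation in situations where Section 3.2.3 requires follow-up. The CKD item is ambiguous among three readings. Followed literally, Section 1 and the synopsis lose later week-6 and week-12 outcomes in randomised patients for reasons that may be related to treatment or outcome.

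The size cannot be derived from the documents and may be small with 40 patients over 12 weeks. It is tempting to add that missingness will differ by arm. That is a risk, not a finding, since no withdrawal rate by arm is given. Whether bias arises depends on two things the plan leaves open: whether the value that triggered stopping is kept, and whether withdrawn patients stay in the analysis.

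**What to change.** Leave the treatment-stopping rules as they are, and reconcile the synopsis, Section 1 and Section 3.2.3:

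1. Treat stopping study drug, leaving the study and exclusion from analysis as three separate events, and say which one each rule means, including the CKD item.
2. State that patients who stop study drug are still asked to attend the scheduled week-6 and week-12 outcome visits, subject to the two consent exceptions in Section 3.2.3 and the investigator's judgement of the patient's interest.
3. State in Section 5 that all randomised patients are analysed in their assigned arm with all data collected, including the value that triggered stopping.

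The cost is protocol wording and a few already-scheduled visits for patients who are off study drug.
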